8.4 Retention of Samples for Future Research

Plasma, serum, and urine samples will be retained for future research purposes as indicated in the [Schedule of Assessments](#). These samples may be used to enable development and measurement of additional exploratory biomarkers in the future. Samples for future research will be stored at – 80°C by CSL and retained for up to 10 years. These assessments will not be captured in the clinical database, and will be analyzed and reported separately. Future biomarker analyses may include, but is not limited to, transcriptome profile in peripheral whole blood.

Refer to the laboratory manual for further details about the collection, shipment, storage, and destruction of samples for future research.

8.5 Concomitant Therapies

All drug therapies administered to a subject up to 12 weeks before signing the ICF must be documented in the eCRF. All drugs and / or procedures currently being administered to a subject at the time of signing the ICF, and which continue to be taken in addition to CSL346 during the study, are regarded as concomitant therapies and must be documented in the eCRF. Refer to [Section 7.2](#) and [Section 7.3](#), respectively, for permitted and prohibited concomitant therapies.

8.6 Visit Schedule

8.6.1 Assessment Time Windows

Time windows for all visits and assessments are detailed in [Table 10](#).

Table 10 Time Windows for Visits and Assessments

Visit / Procedure	Time Window (Relative to Scheduled Visit / Procedure)
Visit 1 (Up to –6 weeks; Screening)	Not applicable
Visit 2 (Day –21; Screening)	± 7 days
Visit 3 (Day –7; Lead-in)	± 4 days
Visit 4 (Day 1)	Not applicable
Visit 4 Vital signs	± 15 minutes
Visits 5, 6, and 7 (Weeks 1, 2, and 4)	± 3 days
Visits 8 and 9 (Weeks 8 and 12)	± 5 days
Visit 10 (Week 16; Follow-up)	± 7 days
EOS (Week 24; Follow-up)	± 7 days
PK Blood Sampling Time Points	Serial blood samples for PK will be collected at Visit 4 (Day 1) predose, at 30 (± 5 minutes), 60 (± 10 minutes), and 120 (± 10 minutes) minutes after the first IV dose of IP (before the first SC dose of IP) is administered, then after the final vital signs measurement. Single PK samples will also be collected at all subsequent visits (before treatment on SC dosing days).

EOS = End of Study; IP = investigational product; IV = intravenous; PK = pharmacokinetic; SC = subcutaneous.

8.6.2 Screening

8.6.2.1 Screening Visit 1 (Visit 1, ≤ 63 days before Day 1)

All subjects must provide written informed consent before any study-specific assessments or procedures are performed. Written informed consent is not required for assessments or procedures performed according to SOC (eg, for diagnosis or treatment); results from such assessments may be used in the determination of study eligibility.

The following procedures will be conducted and documented at Screening Visit 1:

- Obtain written informed consent and register the subject via the IRT
- Confirm and document that the subject conforms with inclusion / exclusion criteria
- Obtain demographic information
- Obtain medical history
- Perform serum pregnancy test (FCBP only)
- Measure vital signs (BP in triplicate)
- Measure height and weight

- Perform 12-lead ECG (triplicate)
- Confirm LVEF based on local ECHO. An ECHO performed for nonstudy-related reasons within 3 months before Screening can be used.
- Collect blood samples for the following:
 - Viral serology
 - Standard hematology and biochemistry testing
 - Troponin-I and BNP
 - Coagulation
- Collect urine sample for standard urinalysis
- Collect subject's timed 24-hour urine sample (leading up to the morning of Screening)
- Collect information on AEs since signing the ICF
- Collect information on prior (within the previous 30 days) / concomitant therapies

The procedures for handling Screen Failures are described in [Section 4.2](#).

8.6.2.2 Screening Visit 2 (Visit 2, Day -21)

Screening Visit 2 should be performed within 6 weeks after Screening Visit 1. The following procedures will be conducted and documented at Screening Visit 2:

- Confirm and document that the subject conforms with inclusion / exclusion criteria
- Perform complete physical examination
- Measure BP (triplicate)
- Collect blood sample for SCr only
- Collect information on AEs
- Collect information on concomitant therapies
- Perform SC normal saline test infusion
- Remind subject to collect FMV urine samples for 3 days leading up to the next visit and to arrive after a minimum 6-hour fast

8.6.3 Lead-in (Visit 3, Day –7)

The following procedures will be conducted and documented at the second Lead-in Visit (Visit 3):

- Confirm and document that the subject conforms with randomization criteria for BP, SCr, and troponin
- Perform serum or urine pregnancy test (FCBP only)
- Perform abbreviated physical examination
- Measure vital signs (BP in triplicate)
- Measure weight
- Perform 12-lead ECG (triplicate)
- Collect blood samples for the following:
 - Standard hematology and biochemistry testing
 - Troponin-I and BNP
 - Biomarker analysis
- Collect urine samples for the following:
 - FMV (for Days –9, –8, and –7)
 - Morning midstream
- Collect information on AEs
- Collect information on concomitant therapies
- Remind subject to collect FMV urine samples for 3 days leading up to the next visit and to arrive after a minimum 6-hour fast

8.6.4 Treatment

8.6.4.1 Treatment Visit 4 (Day 1)

8.6.4.1.1 Before Administration of IP

Subjects who complete all Screening assessments and who satisfy the randomization criteria will be enrolled into the study and randomized. After randomization, the following procedures are to be conducted and documented at Visit 4 before administration of IP:

- Confirm and document that the subject conforms with randomization criterion for BP
- Perform serum or urine pregnancy test (FCBP only)
- Perform abbreviated physical examination
- Measure vital signs (BP in triplicate)
- Measure weight
- Perform 12-lead ECG (triplicate)
- Collect blood samples for the following:
 - Standard hematology and biochemistry testing
 - Troponin-I and BNP
 - HbA1c
 - Immunogenicity
 - Biomarker analysis
- Collect blood sample for PK before dosing
- Collect urine samples for the following:
 - FMV (for Days -2, -1, and 1)
 - Morning midstream
 - Standard urinalysis
- Collect information on AEs
- Collect information on concomitant therapies

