4.1.3 Randomization Criteria

To be randomized into the study, subjects must meet the following Randomization Criteria at Visit 3 (Day -7) and Visit 4 (Day 1):

1. $SBP \leq 150$ mmHg and $DBP \leq 100$ mmHg at Visit 3 (Day -7) and Visit 4 (Day 1). If the subject's BP at Visit 3 (Day -7) or Visit 4 (Day 1) does not satisfy this criterion, randomization / treatment should be delayed and FMV urine samples discarded. The Investigator should ensure the subject is compliant with concomitant antihypertensive medications and can repeat this BP evaluation within 3 to 10 days of the failed criterion. The subject will be instructed to collect 3 additional FMV urine samples.
 - If a subject satisfies the BP criterion at the rescheduled visit, the subject can be randomized.
 - If a subject fails to satisfy the BP criterion at the rescheduled visit, the subject will be considered a Lead-in failure (discontinued from study) and will not be re-screened
 - If a subject fails to satisfy the BP criterion at any 2 visits (including Visit 3, Visit 4, and the rescheduled visit), the subject will also be considered a Lead-in failure (discontinued from study) and will not be re-screened

2. Change in SCr from Visit 2 (Day -21) to Visit 3 (Day -7) ≤ 0.3 mg/dL (26.5 $\mu\text{mol/L}$) by central lab assessment. Subjects who do not satisfy this criterion may have 1 repeat SCr test performed at an unscheduled visit within 1 week after Visit 3 (Day -7); for these subjects, the randomization criterion will be evaluated based on change in SCr from Visit 3 (Day -7) to the unscheduled visit (≤ 0.3 mg/dL change by central lab assessment). Subjects who qualify must return for randomization (Visit 4 / Day 1) within 1 week after the unscheduled visit. Subjects who do not qualify will be considered a Lead-in failure (discontinued from the study) and will not be re-screened.
3. Troponin-I levels \leq URL at Visit 3 (Day -7).

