8.6.4.1.2 Administration of IP and After

The following additional procedures are to be conducted and documented at Visit 4 as related to administration of IP:

- Randomization and IRT IP assignment
- Administer IV loading dose of IP
- Measure vital signs (BP in triplicate) at 30, 60, and 120 minutes after IV dose
- At least 2 hours (but no more than 6 hours) after IV dose, administer the first SC dose

- Measure vital signs (BP in triplicate) at 30 and 60 minutes after SC dose
- Collect serial PK blood samples according to [Table 10](#)
- Collect information on AEs, including local tolerability assessment
- Remind subject to collect a 24-hour timed urine sample beginning on the morning of Day 7 and continuing until the morning of Day 8

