10.3.1 Subject Disposition and Characteristics

10.3.1.1 Subject Disposition

Summary tables by treatment group (8 mg/kg CSL346, 16 mg/kg CSL346, CSL346 combined, and placebo) and total population will present the following:

- The number of subjects enrolled into the study (ie, signed the ICF)
- The number of subjects randomized and who were withdrawn due to failure to meet the Randomization Criteria
- The number of subjects who received IP
- The number of subjects who prematurely discontinued IP
- The number of subjects who were withdrawn from the study
- The number of subjects who completed the study

Similar tables will also be provided for each strata (ie, the use of concomitant SGLT2 inhibitors).

Reasons for discontinuing the IP and withdrawing a subject from the study will be listed by subject.

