### **8.2 General Derived Variables**

#### **8.2.1 Reference Dates and Study Days**

Reference dates are used to assign study periods relative to treatment ([Section 8.4](#)).

- The safety reference date is the treatment start date (date of IV loading dose), and will be used to calculate study day for safety measures.
- The efficacy reference date is the randomization date and will be used to calculate study day for efficacy measures.

- The PK reference date is the date and time of the IV loading dose and will be used to calculate study day/time for PK measures.

The respective study day will be calculated as (date of interest - reference date) + 1 if the date of interest occurs on or after the reference date. If the date of interest occurs before the reference date, then the study day will be calculated as (date of interest – reference date).

There will be no study day zero.

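### Protocol 8.6.4.1.1 puts the Visit 4 blood-pressure check after randomization, contradicting 4.1.3 and 8.6.4.1.2; a site that follows it literally can randomize a subject who then fails the criterion

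*Protocol*

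**What the plan says.** Four places in the protocol bear on the order of events at Visit 4.

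- **Section 4.1.3** makes the criteria a condition of entry: "To be randomized into the study, subjects must meet the following Randomization Criteria at Visit 3" and at Visit 4. If the blood pressure fails at either visit, "randomization / treatment should be delayed and FMV urine samples discarded". The reading may be repeated 3 to 10 days later. A subject who passes the repeat can then be randomized. One who fails it is a lead-in failure and leaves the study.
- **Section 8.6.4.1.1** opens consistently with that: "Subjects who complete all Screening assessments and who satisfy the randomization criteria will be enrolled into the study and randomized". The next sentence reads "After randomization, the following procedures are to be conducted and documented at Visit 4 before administration of IP". The list beneath it begins "Confirm and document that the subject conforms with randomization criterion for BP" and includes the pregnancy test, the triplicate blood pressure and the first-morning-void (FMV) urine samples.
- **Section 8.6.4.1.2**, which covers dosing and afterwards, begins with "Randomization and IRT IP assignment". Randomization therefore appears a second time, after those checks.
- **Section 10.3.1.1** plans a disposition row: "The number of subjects randomized and who were withdrawn due to failure to meet the Randomization Criteria".

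Anyone given a randomization number belongs to the ITT set, which is used for the primary analysis (protocol 10.2.2, SAP 6.2).

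**The concern.** The Visit 4 blood pressure is measured in the list that 8.6.4.1.1 places after randomization. The opening sentence of that section therefore does not resolve the conflict: at that point the site does not yet have the reading that decides whether the subject qualifies. Sections 4.1.3 and 8.6.4.1.1 cannot both be followed as written, and the visit list is the text a site works from on the day.

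ITT membership cannot be undone. A subject randomized first and found to fail afterwards would be sent away for a repeat reading. A second failure would make that subject a lead-in failure although already randomized, yet SAP 8.4 ends the Lead-in Period at randomization. Such a subject would use up an allocation, probably receive no dose and probably supply no post-baseline ACR.

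The missing-data sensitivity analysis would not cover this subject. SAP 10.1.3 runs the tipping-point analysis on the Per-Protocol set, and SAP 16.7 removes all data from subjects who received no dose.

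**Working it through.** **1. The order in each place.**

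| Place | Visit 4 blood-pressure criterion relative to randomization |
|---|---|
| Protocol 4.1.3 | Before: a condition of being randomized |
| Protocol 8.6.4.1.1, opening sentence | Before: only subjects who satisfy the criteria are randomized |
| Protocol 8.6.4.1.1, work list | After |
| Protocol 8.6.4.1.2 | Before: randomization is listed after the 8.6.4.1.1 checks |
| Protocol 10.3.1.1 | Open: provides for subjects randomized and then withdrawn for failing the criteria |

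The work list stands against the rest. This is a contradiction on sequence.

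**2. Reproducing the planned sample size.** Inputs from protocol 10.1: SD 0.65; effect ln(1 − 0.27) = −0.315; one-sided alpha 0.10; power 85%; 94 evaluable subjects; 6% drop-out; a ceiling of 124 randomized. The 1:1:2 allocation is 1:1 for pooled CSL346 against placebo, so 47 per group.

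- Standard error: 0.65 × √(2/47) = 0.134.
- Power: 85.7% by the normal approximation, 85.4% by the noncentral t. The plan states 85%.
- Smallest significant difference, by t: 0.173, or −15.9%. The plan states −0.173, about −16%.
- Randomized: 94 / (1 − 0.06) = 100.

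The plan's figures reproduce.

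**3. Effect of randomizing subjects who then fail.** Let f be the share of randomized subjects who fail for good and supply no post-baseline ACR. The documents give no value, so f is an assumption. The 6% drop-out is applied to the rest.

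- Completers from 100 randomized = 100 × (1 − f) × 0.94
- SE = 0.65 × 2 / √(completers)
- Randomized needed for 94 completers = 94 / [0.94 × (1 − f)], rounded up

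| f (assumed) | Completers of 100 | SE | Power (t) | Randomized for 94 completers |
|---|---|---|---|---|
| 0% | 94.0 | 0.134 | 85.4% | 100 |
| 2% | 92.1 | 0.135 | 84.9% | 103 |
| 5% | 89.3 | 0.138 | 84.0% | 106 |
| 10% | 84.6 | 0.141 | 82.5% | 112 |
| 15% | 79.9 | 0.145 | 80.8% | 118 |

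The ceiling of 124 absorbs f up to 1 − 94 / (0.94 × 124) = 19%.

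**4. What reaches the primary model.** The response in the mixed model is change from baseline in log ACR. A randomized subject with no post-baseline ACR contributes no record. The ITT count exceeds the number analysed, and the standard error rises as in step 3.

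**The case against.** The strongest reply is that this is one misplaced phrase. Section 4.1.3, the opening sentence of 8.6.4.1.1 and the list in 8.6.4.1.2 all put the criteria first. Sections 3.1.2 and 3.5 also make a subject eligible for randomization only once the randomization criteria are met. The IRT may already refuse a number until the criterion is confirmed; protocol 6.2 refers to randomization specifications that are not among these documents. This stands to the extent that the consequence is conditional on a site following the list literally. It does not remove the contradiction.

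A reader might infer more than the documents support:

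- **That ineligible subjects will enter the ITT set without outcome data.** A failed reading leads first to a repeat, and subjects who pass it continue. Protocol 4.3.2 attempts Visit 10 and the final visit for withdrawn subjects.
- **That the plan expects this to happen.** The disposition row in 10.3.1.1 names neither Visit 4 nor blood pressure and works equally well as a count of deviations.
- **That the treatment comparison is biased.** The check is pre-dose and blinded, so the loss should not depend on arm. The treatment-policy strategy in SAP 10.1.1 already names non-initiation of treatment.
- **That the drop-out allowance is used up.** Protocol 4.3.4 allows up to 124 randomized in order to reach 94 completers.
- **That delayed dosing distorts the Week 16 result.** SAP 8.2.1 says "The efficacy reference date is the randomization date and will be used to calculate study day for efficacy measures", while safety study day runs from the IV loading dose. For a subject randomized before a 3-to-10-day delay, the two would differ by about that much. But SAP 8.2.5 analyses nominal visits without windows, and the model treats visit as categorical. Replacement FMV samples collected after randomization would still be pre-dose and blinded, and the baseline is defined by values before treatment.

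**Conclusion.** The point holds as an internal contradiction in the operative Visit 4 instructions. The work list in 8.6.4.1.1 conflicts with 4.1.3 and 8.6.4.1.2 on whether the blood-pressure criterion is confirmed before or after randomization. A site following the list can create an ITT subject who fails the criterion, is probably never dosed and is outside the tipping-point analysis.

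The statistical cost is small. At an assumed 2% to 5%, power with 100 randomized falls by 0.5 to 1.4 percentage points, and 3 to 6 more subjects would have to be randomized to restore 94 completers. This rests on the plan's SD of 0.65, its 6% drop-out and an assumed failure rate. No directional bias is shown. It is worth correcting because the loss is avoidable and an allocation, once issued, cannot be removed from the ITT set.

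**What to change.** - In 8.6.4.1.1, change the lead-in to the work list so that the procedures are done before randomization, in agreement with 4.1.3.
- List randomization once only, in 8.6.4.1.2, after those checks.
- Have the IRT require confirmation of the Visit 4 criterion before it issues a number. If its specifications already do so, only the wording needs to change.
- Keep the disposition row in 10.3.1.1 and label it as a count of deviations. Deleting it would hide any case that did occur.

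The cost is a wording change and at most one IRT entry check. The same procedures are done on the same day, and no blood-pressure threshold or clinical rule changes.

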8.6.4.1.2 Administration of IP and After

The following additional procedures are to be conducted and documented at Visit 4 as related to administration of IP:

- Randomization and IRT IP assignment
- Administer IV loading dose of IP
- Measure vital signs (BP in triplicate) at 30, 60, and 120 minutes after IV dose
- At least 2 hours (but no more than 6 hours) after IV dose, administer the first SC dose

- Measure vital signs (BP in triplicate) at 30 and 60 minutes after SC dose
- Collect serial PK blood samples according to [Table 10](#)
- Collect information on AEs, including local tolerability assessment
- Remind subject to collect a 24-hour timed urine sample beginning on the morning of Day 7 and continuing until the morning of Day 8

8.6.4.2 Treatment Visit 5 (Week 1, Day 8)

The following procedures are to be conducted and documented at Visit 5:

- Perform abbreviated physical examination
- Measure vital signs (BP in triplicate)
- Measure weight
- Perform 12-lead ECG (triplicate)
- Collect blood samples for the following:
 - Standard hematology and biochemistry testing
 - Troponin-I and BNP
- Collect trough PK blood sample
- Collect subject's timed 24-hour urine sample (for Day 7 to Day 8)
- Collect information on AEs, including local tolerability assessment
- Collect information on concomitant therapies
- Remind subject to collect FMV urine samples for 3 days leading up to the next visit

8.6.4.3 Treatment Visit 6 (Week 2, Day 15)

The following procedures are to be conducted and documented at Visit 6:

- Perform abbreviated physical examination
- Measure vital signs (BP in triplicate)
- Measure weight
- Perform 12-lead ECG (triplicate)

- Collect blood samples for the following:
 - Standard hematology and biochemistry testing
 - Troponin-I and BNP
- Collect PK blood sample
- Collect urine samples for FMV (for Days 13, 14, and 15)
- Collect information on AEs, including local tolerability assessment
- Collect information on concomitant therapies
- Remind subject to collect FMV urine samples for 3 days leading up to the next visit and to arrive after a minimum 6-hour fast

8.6.4.4 Treatment Visit 7 (Week 4, Day 29)

8.6.4.4.1 Before Administration of IP

The following procedures are to be conducted and documented at Visit 7 before administration of IP:

- Perform serum or urine pregnancy test (FCBP only)
- Perform abbreviated physical examination
- Measure vital signs
- Measure weight
- Perform 12-lead ECG (triplicate)
- Collect blood samples for the following:
 - Standard hematology and biochemistry testing
 - Troponin-I and BNP
 - Immunogenicity
 - Biomarker analysis
- Collect trough PK blood sample
- Collect urine samples for the following:
 - FMV (for Days 27, 28, and 29)

- Morning midstream
- Collect information on AEs, including local tolerability assessment
- Collect information on concomitant therapies

8.6.4.4.2 Administration of IP and After

The following additional procedures are to be conducted and documented at Visit 7 as related to administration of IP:

- IRT IP assignment
- Administer the second SC dose of IP
- Collect information on AEs, including local tolerability assessment
- Remind subject to collect FMV urine samples for 3 days leading up to the next visit and to arrive after a minimum 6-hour fast

8.6.4.5 Treatment Visit 8 (Week 8, Day 57)

8.6.4.5.1 Before Administration of IP

The following procedures are to be conducted and documented at Visit 8 before administration of IP:

- Perform serum or urine pregnancy test (FCBP only)
- Perform abbreviated physical examination
- Measure vital signs (BP in triplicate)
- Measure weight
- Perform 12-lead ECG (triplicate)
- Collect blood samples for the following:
 - Standard hematology and biochemistry testing
 - Troponin-I and BNP
 - Immunogenicity
 - Biomarker analysis
- Collect trough PK blood sample

- Collect urine samples for the following:
 - FMV (for Days 55, 56, and 57)
 - Morning midstream
- Collect information on AEs, including local tolerability assessment
- Collect information on concomitant therapies

8.6.4.5.2 Administration of IP and After

The following additional procedures are to be conducted and documented at Visit 8 as related to administration of IP:

- IRT IP assignment
- Administer the third SC dose of IP
- Collect information on AEs, including local tolerability assessment
- Remind subject to collect FMV samples on Day 83 and Day 84, to collect a 24-hour urine sample beginning on the morning of Day 84 and continuing until the morning of Day 85

8.6.4.6 Treatment Visit 9 (Week 12, Day 85)

8.6.4.6.1 Before Administration of IP

The following procedures are to be conducted and documented at Visit 9 before administration of IP:

- Perform serum or urine pregnancy test (FCBP only)
- Perform abbreviated physical examination
- Measure vital signs (BP in triplicate)
- Measure weight
- Perform 12-lead ECG (triplicate)
- Collect blood samples for the following:
 - Standard hematology and biochemistry testing
 - Troponin-I and BNP
 - Biomarker analysis

- Collect trough PK blood sample
- Collect urine samples for the following:
 - FMV (for Days 83 and 84)
 - Timed 24-hour urine sample (for Day 84 to 85)
- Collect information on AEs, including local tolerability assessment
- Collect information on concomitant therapies

